 - 3 I have lost 5 pounds or more.
9. Increased Weight (Within the Last Two Weeks):
 - 0 I have not had a change in my weight.
 - 1 I feel as if I've had a slight weight gain.
 - 2 I have gained 2 pounds or more.
 - 3 I have gained 5 pounds or more.
10. Concentration/Decision Making:
 - 0 There is no change in my usual capacity to concentrate or make decisions.
 - 1 I occasionally feel indecisive or find that my attention wanders.
 - 2 Most of the time, I struggle to focus my attention or to make decisions.
 - 3 I cannot concentrate well enough to read or cannot make even minor decisions.

11. View of Myself:

- 0 I see myself as equally worthwhile and deserving as other people.
- 1 I am more self-blaming than usual.
- 2 I largely believe that I cause problems for others.
- 3 I think almost constantly about major and minor defects in myself.

12. Thoughts of Death or Suicide:

- 0 I do not think of suicide or death.
- 1 I feel that life is empty or wonder if it's worth living.
- 2 I think of suicide or death several times a week for several minutes.
- 3 I think of suicide or death several times a day in some detail, or I have made specific plans for suicide or have actually tried to take my life.

13. General Interest:

- 0 There is no change from usual in how interested I am in other people or activities.
- 1 I notice that I am less interested in people or activities.
- 2 I find I have interest in only one or two of my formerly pursued activities.
- 3 I have virtually no interest in formerly pursued activities.

14. Energy Level:

- 0 There is no change in my usual level of energy.
- 1 I get tired more easily than usual.
- 2 I have to make a big effort to start or finish my usual daily activities (for example, shopping, homework, cooking or going to work).
- 3 I really cannot carry out most of my usual daily activities because I just don't have the energy.

15. Feeling slowed down:

- 0 I think, speak, and move at my usual rate of speed.
- 1 I find that my thinking is slowed down or my voice sounds dull or flat.
- 2 It takes me several seconds to respond to most questions and I'm sure my thinking is slowed.
- 3 I am often unable to respond to questions without extreme effort.

16. Feeling restless:

- 0 I do not feel restless.
- 1 I'm often fidgety, wringing my hands, or need to shift how I am sitting.
- 2 I have impulses to move about and am quite restless.
- 3 At times, I am unable to stay seated and need to pace around.

To Score:

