### 12.7.3 Health-related Quality of Life Endpoints

The Health Outcome/Quality of Life endpoints are the change from baseline in the following health outcome/QoL assessments at Weeks 12, 16, and 24:

- Quick Inventory of Depressive Symptomatology-Self Report (16 Items) (QIDS-SR16) total score. The total score (range 0-27) is calculated as the sum of the following 9 items: Highest score on any sleep items (Q1-Q4), Q5, highest score on any appetite/weight items (Q6-Q9), Q10, Q11, Q12, Q13, Q14, highest score on either psychomotor items (Q15 & Q16). The total score will be considered as missing if any of the component score is missing.
- The Dermatology Life Quality Index (DLQI) total score (0-30) will be calculated as the sum of 10 questions with each ranging from 0 to 3. The scoring of each answer is as follows:

Very much	Scored 3
A lot	Scored 2
A little	Scored 1
Not at all	Scored 0
Not relevant	Scored 0
Question unanswered	Scored 0
Question 7: "prevented work or studying"	Scored 3

If one question is left unanswered this is scored 0 and the scores are summed and expressed as usual out of a maximum of 30. If two or more questions are left unanswered the total DLQI score is missing. If question 7a is answered 'no' or 'not relevant', then the answer of 7b will be ignored. Additionally, the score of each of 6 domains (daily activities, personal relationships, symptoms and feelings, leisure, work/school, and treatment) will be summarized separately.

- The SF-12 summary scales will be calculated using the SF-12 Health Survey Standard Scoring software. Summary scores will be computed for Physical Summary (PCS) and Mental Summary (MCS). Subscores will also be computed for the following 8 domains:
  - Physical Functioning (PF)
  - Role-Physical (RP)
  - Bodily Pain (BP)

- Social Functioning (SF)
  - Mental Health (MH)
  - Role-Emotional (RE)
  - Vitality (VT)
  - General Health (GH)
- Work Productivity and Activity Impairment Questionnaire: Psoriasis (WPAI:PSO) score. WPAI-PSO outcomes are expressed as impairment percentages, with higher numbers indicating greater impairment and less productivity, i.e., worse outcomes as follows
    - The percent work time missed due to psoriasis will be summarized for all subjects who answer “Yes” to Question 1, “Are you currently employed?”. This will be calculated using the following formula:  $100 * ((\text{Question 2}) / (\text{Question 2} + \text{Question 4}))$

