### **12.8.3 Health-related Quality of Life Analyses**

All QoL endpoints will be summarized by visit and treatment group using descriptive statistics on the FAS population.

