Median	XX	XX	XX	XX
75th percentile	XX	XX	XX	XX
Log Rank Test p-Values				
PPC-06 vs. Placebo	0.XXX	0.XXX	0.XXX	
PPC-06 vs. PPC-06 600 mg BID	0.XXX	0.XXX		
PPC-06 vs. PPC-06 400 mg BID	0.XXX			

Note: PASI= Psoriasis Area and Severity Index

[1] Days from baseline to first achieving a reduction of 75% or greater from Baseline in PASI. Subjects who did not achieve PASI-75 by the last assessment or withdrew prior to the last study visit will be censored at their last PASI assessment.

Generated on XX/XX/XX:XXXX by XXXXX / Uses: XXXX / Reference: Listings XXXX

Table 14.2.2.11: Analysis of Secondary Efficacy Outcome  
 Time to Achieving an IGA Score of Clear or Almost Clear  
 Full Analysis Set, OC

	PPC-06 400 mg QD (N=XX)	PPC-06 400 mg BID (N=XX)	PPC-06 600 mg BID (N=XX)	Placebo (N=XX)
Time to Achieving an IGA Score of Clear or Almost Clear [1]				
Kaplan-Meier Estimates				
N	XX	XX	XX	XX
25th percentile	XX	XX	XX	XX
Median	XX	XX	XX	XX
75th percentile	XX	XX	XX	XX
Log Rank Test p-Values				
PPC-06 vs. Placebo	0.XXX	0.XXX	0.XXX	
PPC-06 vs. PPC-06 600 mg BID	0.XXX	0.XXX		
PPC-06 vs. PPC-06 400 mg BID	0.XXX			

Note: IGA= Investigator's Global Assessment

[1] Days from baseline to first achieving an IGA score of 0 or 1. Subjects who did not achieve an IGA of 0 or 1 at the last assessment or withdrew prior to the last study visit will be censored at their last IGA assessment.

Generated on XX/XX/XX:XXXX by XXXXX / Uses: XXXX / Reference: Listings XXXX

Table 14.2.3.1: Analysis of Quality of Life Outcome  
Change from Baseline in QIDS-SR16 Total Score by Visit  
Full Analysis Set, OC

	PPC-06 400 mg QD (N=XX)	PPC-06 400 mg BID (N=XX)	PPC-06 600 mg BID (N=XX)	Placebo (N=XX)
Baseline				
N	XX	XX	XX	XX
Mean (SD)	XX.X (XX.X)	XX.X (XX.X)	XX.X (XX.X)	XX.X (XX.X)
Median	XX	XX	XX	XX
Minimum, Maximum	XX, XX	XX, XX	XX, XX	XX, XX
Week 12				
N	XX	XX	XX	XX
Mean (SD)	XX.X (XX.X)	XX.X (XX.X)	XX.X (XX.X)	XX.X (XX.X)
Median	XX	XX	XX	XX
Minimum, Maximum	XX, XX	XX, XX	XX, XX	XX, XX
Change from baseline				
N	XX	XX	XX	XX
Mean (SD)	XX.X (XX.X)	XX.X (XX.X)	XX.X (XX.X)	XX.X (XX.X)
Median	XX	XX	XX	XX
Minimum, Maximum	XX, XX	XX, XX	XX, XX	XX, XX
<Repeat for Week 16, Week 24>				

Note: QIDS-SR16=Quick Inventory of Depressive Symptomatology-Self Report (16 Items). OC = Observed Cases.

Generated on XX/XX/XX:XXXX by XXXXXX / Uses: XXXX / Reference: Listings XXXX

Table 14.2.3.2.1: Analysis of Quality of Life Outcome  

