[PPC-06 400 mg QD] [ PPC-06 400 mg BID] [ PPC-06 600 mg BID] [Placebo]

Subject Number	Analysis Visit	Visit Date (Day) [1]	Type	Value	CFBL
XX-XXX	Baseline	DDMMYYYYY(XX)	Observed	3 – Moderate	--
	Week 4	DDMMYYYYY(XX)	Observed	2 – Mild	-1
	Week 8	DDMMYYYYY(XX)	Observed	2 – Mild	-1
	Week 12	DDMMYYYYY(XX)	Observed	1 – Almost clear	-2
	Week 16	DDMMYYYYY(XX)	Observed	1 – Almost clear	-2
XX-XXX	Baseline	DDMMYYYYY(XX)	Observed	3 – Moderate	--
	Week 4	DDMMYYYYY(XX)	Observed	3 – Moderate	X
	Week 8	DDMMYYYYY(XX)	Observed	2 – Mild	-1
	Week 12	--	LOCF	2 – Mild	-1
	Week 16	DDMMYYYYY(XX)	Observed	XXX	X
	Week 20	DDMMYYYYY(XX)	Observed	XXX	X
	Week 24	DDMMYYYYY(XX)	Observed	XXX	X

Note: LOCF=Last observation-carried forward. CFBL=Change from baseline calculated as post-baseline minus baseline.

[1] Study day is calculated relative to the date of first study drug administration (Day 1).

Generated on XX/XX/XX:XXXX by XXXXX / Uses: XXXX

Listing 16.2.6.7: Itch by NRS  
 All Randomized Subjects  
 [PPC-06 400 mg QD] [ PPC-06 400 mg BID] [ PPC-06 600 mg BID] [Placebo]

Subject Number	Analysis Visit	Visit Date (Day) [1]	Type	Value	CFBL
XXX-XXX	Baseline	DDMMYYYY (XX)	Observed	X	-
	Week 4	DDMMYYYY (XX)	Observed	X	X
	Week 8	-	LOCF	X	X
	Week 12	DDMMYYYY (XX)	Observed	X	X
	Week 16	DDMMYYYY (XX)	Observed	X	X
	Week 20	DDMMYYYY (XX)	Observed	X	X
	Week 24	DDMMYYYY (XX)	Observed	X	X
	<Etc.>				

Note: NRS = Numerical Rating Scale. LOCF=Last observation-carried forward. CFBL=Change from baseline calculated as post-baseline minus baseline.

[1] Study day is calculated relative to the date of first study drug administration (Day 1).

Generated on XX/XX/XX:XXXX by XXXX/ Uses: XXXX

Listing 16.2.6.8: Self-Report Quick Inventory of Depressive Symptomatology (QIDS-SR16)  
All Randomized Subjects  
[PPC-06 400 mg QD] [ PPC-06 400 mg BID] [ PPC-06 600 mg BID] [Placebo]

Subject Number	Analysis Visit	Visit Date (Day) [1]	Q1	Q2	Q3	Q4	Q5	Q6	Q7	Q8	Q9	Q10	Q11	Q12	Q13	Q14	Q15	Q16	Total	
																			Value	CFBL
XX-XXX	Baseline	DDMMMYYYY(XX)	0	0	0	2	1	1	1	3	0	1	1	1	1	1	1	1	X	X
	Week 12	DDMMMYYYY(XX)	1	1	1	3	2	1	1	3	1	1	1	1	1	1	1	1	X	X
	Week 16	DDMMMYYYY(XX)	1	0	0	1	0	0	0	1	1	0	0	0	0	0	0	0	X	X
	Week 24	DDMMMYYYY(XX)	1	0	0	1	0	0	0	1	1	0	0	0	0	0	0	0	X	X
	Etc.																			

Note: CFBL=Change from baseline calculated as post-baseline minus baseline.

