1. Falling asleep; 2. Sleep during the night, 3. Waking up too early; 4. Sleeping too much 5. Feeling sad, 6. Decreased appetite, 7. Decreased appetite 8. Decreased weight (within the last two weeks), 9. Increased weight (within the Last two weeks), 10. Concentration/decision making, 11. View of myself, 12. Thoughts of death or suicide,13. General interest, 14. Energy level, 15. Feeling slowed down, 16. Feeling restless

[1] Study day is calculated relative to the date of first study drug administration (Day 1).

Generated on XX/XX/XX:XXXX by XXXXXX / Uses: XXXX

Listing 16.2.6.9.1: Dermatology Life Quality Index (DLQI) Individual Questions  
 All Randomized Subjects  
 [PPC-06 400 mg QD] [ PPC-06 400 mg BID] [ PPC-06 600 mg BID] [Placebo]

Subject Number	Analysis Visit	Visit Date (Day) [1]	Q1	Q2	Q3	Q4	Q5	Q6	Q7	Q8	Q9	Q10
XX-XXX	Baseline	DDMMMYYYY(XX)	X	X	X	X	X	X	X	X	X	X
	Week 12	DDMMMYYYY(XX)	X	X	X	X	X	X	X	X	X	X
	Week 16	DDMMMYYYY(XX)	X	X	X	X	X	X	X	X	X	X
	Week 24	DDMMMYYYY(XX)	X	X	X	X	X	X	X	X	X	X
	Etc.											

[1] Study day is calculated relative to the date of first study drug administration (Day 1).

Generated on XX/XX/XX:XXXX by XXXXX / Uses: XXXX

Listing 16.2.6.9.2: Dermatology Life Quality Index (DLQI) Domains and Total Score  
 All Randomized Subjects  
 [PPC-06 400 mg QD] [ PPC-06 400 mg BID] [ PPC-06 600 mg BID] [Placebo]

Subject Number	Analysis Visit	Visit Date (Day) [1]	Symptoms and Feelings		Daily Activities		Leisure		Work and School	Personal Relationships		Treatment	Total	
			Value	CFBL	Value	CFBL	Value	CFBL	Value	Value	CFBL	Value	Value	CFBL
XX-XXX	Baseline	DDMMYYYY(XX)	X	--	X	--	X	--	X	X	--	X	X	--
	Week 12	DDMMYYYY(XX)	X	X	X	X	X	X	X	X	X	X	X	X
	Week 16	DDMMYYYY(XX)	X	X	X	X	X	X	X	X	X	X	X	X
	Week 24	DDMMYYYY(XX)	X	X	X	X	X	X	X	X	X	X	X	X
XX-XXX	Baseline	DDMMYYYY(XX)	X	--	X	--	X	--	X	X	--	X	X	--
	Week 12	DDMMYYYY(XX)	X	X	X	X	X	X	X	X	X	X	X	X
	Week 16	DDMMYYYY(XX)	X	X	X	X	X	X	X	X	X	X	X	X
	Etc													

Note: CFBL=Change from baseline calculated as post-baseline minus baseline.

Symptoms and Feelings includes Q1 and Q2; Daily Activities includes Q3 and Q4; Leisure includes Q5 and Q6; Work and School includes Q7 and Q7a; Personal Relationships includes Q 8 and Q9; Treatment includes Q10

[1] Study day is calculated relative to the date of first study drug administration (Day 1).

Generated on XX/XX/XX:XXXX by XXXXX / Uses: XXXX

Listing 16.2.6.10.1: SF-12 Subdomains  
 All Randomized Subjects  

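### No planned table counts answers to the QIDS-SR16 suicide item by arm; they appear only in a by-subject listing

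*SAP*

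**What the plan says.** Protocol Appendix 7 reproduces the form. Item 12 is scored 0 to 3. A score of 2 reads "I think of suicide or death several times a week for several minutes". A score of 3 begins "I think of suicide or death several times a day in some detail, or I have made specific plans for suicide" and extends to an actual attempt.

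Protocol 4.2.2 makes the QIDS-SR16 total score a health outcome/quality-of-life endpoint at Weeks 12, 16 and 24. Protocol 4.2.3 does not list it among the safety endpoints. Protocol Table 1-1 also schedules the questionnaire at the early termination visit (ETV) and at Week 25.

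SAP 12.7.3 defines the score: "The total score (range 0-27) is calculated as the sum of the following 9 items", item 12 being one of the nine. It adds: "The total score will be considered as missing if any of the component score is missing". SAP 12.8.3 sets the analysis: "All QoL endpoints will be summarized by visit and treatment group using descriptive statistics on the FAS population".

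In SAP 16, the one QIDS-SR16 table (14.2.3.1, "Change from Baseline in QIDS-SR16 Total Score by Visit") has rows for baseline and Weeks 12, 16 and 24. It gives N, mean (SD), median, minimum and maximum of the total and of its change, with no item rows and no test. Listing 16.2.6.8 prints Q1 to Q16 for every randomized subject by visit, under an arm heading, and its footnote identifies the column: "12. Thoughts of death or suicide,13. General interest".

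**The concern.** The trial collects a direct question on suicidal thoughts from every arm but plans no by-arm count of the answers. In the only summary the item is one of nine addends. An improvement in sleep or energy can offset a worsening on item 12, and a few subjects who worsen hardly move a total.

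The questionnaire could then be reported as a quality-of-life result while the safety information in one of its items was left for the reader to count from a listing of about 400 subjects with 16 item columns each. Safety and tolerability is a stated secondary objective, Protocol 2.1 names depression among the conditions for which people with psoriasis appear to be at higher risk, and exclusion criterion 25 bars psychiatric syndromes only where they may influence compliance or outcome.

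The SAP already uses the format that is missing here. Table 14.2.3.2.2 gives n (%) by response category and arm for the DLQI Work and School and Treatment domains, the second of which is a single question.

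**Working it through.** The plan states no figure on this point, so there is none to reproduce. The check has four parts.

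**1. Where an item 12 answer can surface.** The inputs are the schedule (Protocol Table 1-1), the windows (SAP 11.4) and the table and listing shells (SAP 16).

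| When answered | Table 14.2.3.1 | Listing 16.2.6.8 |
|---|---|---|
| Baseline, Weeks 12, 16, 24 | Only inside the total | Item 12 shown |
| ETV windowed to Week 12 (Days 71-98), 16 (Days 99-126) or 24 (Day 155 on), within 15 days of last dose | Only inside the total, if nearest the target day | Item 12 shown |
| ETV windowed to Week 4 (to Day 42), 8 (Days 43-70) or 20 (Days 127-154) | No row | Item 12 shown |
| ETV more than 15 days after last dose | Becomes Visit 9; no row | Item 12 shown |
| Week 25 | No row | Item 12 shown |

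SAP 11.4 supplies its own example of the fourth line: last dose on Day 84 and ETV on Day 100, so 100 - 84 = 16 days, and the visit is analysed as Visit 9.

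Week 25 needs one qualification. For a completer, Day 175 is about 7 days after last dose, so it falls in the open-ended Week 24 window. The assessment nearest Day 168 is taken, so the Week 25 answer normally gives way to the Week 24 visit. It would enter only if it fell in a tabulated window with no nearer assessment.

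The listing shell ends in an open continuation after Week 24. I read that as including the remaining visits.

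**2. Dilution in the total.** Item 12 contributes at most 3 of 27 points. If k of n subjects move by s points on item 12 and nothing else changes, the arm mean rises by k × s / n. SAP 7 gives about 100 randomized and 50 completers per arm, so n = 50 and n = 100 bracket the table. The values of k and s are illustrations.

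- 3 subjects, 0 to 2: 3 × 2 / 50 = 0.12; 3 × 2 / 100 = 0.06.
- 3 subjects, 0 to 3: 3 × 3 / 50 = 0.18; 3 × 3 / 100 = 0.09.
- 2 subjects, 0 to 1: 2 × 1 / 50 = 0.04; 2 × 1 / 100 = 0.02.

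The table prints means to one decimal. The first case is worth about one unit in the last digit, and the third can round away.

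The documents give no SD of change. If it were 3 to 4 points (an assumption), the standard error of an arm mean would be 3/√50 = 0.42 to 4/√50 = 0.57 with n = 50, and 3/√100 = 0.30 to 4/√100 = 0.40 with n = 100. For three subjects moving from 0 to 2, that is 0.42/0.12 = 3.5 to 0.57/0.12 = 4.7 times the shift (n = 50), or 0.30/0.06 = 5.0 to 0.40/0.06 = 6.7 times (n = 100).

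The other statistics do not help. A minimum or maximum of the total, or of its change, does not say which component produced it.

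**3. Missing components.** With any one of the nine components missing the total is missing, and QIDS-SR16 is analysed as observed (SAP 9). A subject who answered item 12 but left another required component blank therefore drops out of the table at that visit.

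**4. What a by-arm count would add.** With 3 subjects worsening against 0, the table would read 3/50 (6%) or 3/100 (3%) against none. The two-sided Fisher p is 2 × C(50,3)/C(100,3) = 2 × 19,600/161,700 = 0.24 for n = 50, and 2 × C(100,3)/C(200,3) = 2 × 161,700/1,313,400 = 0.25 for n = 100. About 6 versus 0 is needed for p < 0.05 (0.027 and 0.029). The count makes the cases readable; it does not make them testable.

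**The case against.** The strongest case on the other side is that nothing here is wrong or lost.

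- **The SAP follows the protocol.** The specified endpoint is the total score, scored as the form instructs and summarised descriptively. This stands: there is no contradiction and no faulty method.
- **The item is already output.** Listing 16.2.6.8 shows it by subject and visit within each arm, and a few cases are what a listing can show. This also stands, but a listing leaves the counting to the reader.
- **Adverse events are a second route.** Subjects' responses to questions about their health are one source of adverse events (Protocol 7.5.1.1), and treatment-emergent events are tabulated by arm, system organ class and preferred term (SAP 12.9.1). Ideation recorded as an adverse event would therefore be compared between arms. The limit is that events are sought by nondirective questioning, and the documents contain no rule connecting an item 12 answer to an adverse event record.
- **No drug-specific reason is given.** The documents name flushing, gastrointestinal events, lymphocyte and eosinophil changes, hepatic and renal toxicity, and PML. Depression appears only as a comorbidity of the disease. This stands and limits the weight of the point.
- **Early termination data may be placed elsewhere.** Protocol 8.7.3 assigns ETV data to the closest visit without data, which might bring some answers into the table. It defers to the SAP for details, however, and Protocol 8.10 lets the SAP prevail where the two differ. SAP 11.4 windows by actual study day.

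**Conclusion.** The point holds as a gap in the summary tables. No planned table counts new or worsened item 12 answers by arm, and the total-score table cannot show a few of them: three subjects moving from 0 to 2 change an arm mean by 0.06 to 0.12 of 27 points. Some answers reach no summary at all. How many depends on when subjects stop and on item non-response, neither of which the documents allow one to estimate; the planned 50% dropout means early termination answers could be numerous.

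A reader might infer that suicidal ideation would be invisible in this trial, that arms could not be compared on it, or that the drug is suspected of causing it. The documents support none of these: the listing shows every item by arm, recorded adverse events are tabulated by arm, and no suicidality signal is reported. Nor is the table only a mean, since it also gives SD, median, minimum and maximum.

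The dilution figures rest on illustrative counts, and the comparison with the standard error rests on an assumed SD of 3 to 4. That item 12 is in no table rests on the shells alone. No primary or secondary efficacy inference is affected. This is a cheap improvement, not a correction of an error.

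**What to change.** Add one separate descriptive table on the Safety Population, leaving Table 14.2.3.1 (FAS, observed cases) as it is. By arm it should show:

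- the shift from baseline item 12 score (0, 1, 2, 3) to the worst post-baseline score (0, 1, 2, 3);
- n (%) with any increase from baseline;
- n (%) with an increase to 2 or more;
- the number with no post-baseline answer, so that the denominators are clear.

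Use every post-baseline assessment (Weeks 12, 16, 24, ETV and Week 25), whatever its analysis window and whether or not the total is missing. Show the full shift, because a count limited to scores of 2 or more would miss a new change from 0 to 1. Give no p-value.

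The cost is one shell and one program on data already collected, with no new assessment and no protocol amendment. The downside is an extra table whose small counts can only be read descriptively.

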Generated on XX/XX/XX:XXXX by XXXX/ Uses: XXXX

<Programming Note: The format of protocol deviation listing depends on the actual protocol deviation report form layout. Additional columns may be added, such as "Reference" "Type". If site deviation or deviation for SF subjects are also available, include those at the very end of this listing.>

Listing 16.2.3: Population Datasets  
All Randomized Subjects  
[PPC-06 400 mg QD] [ PPC-06 400 mg BID] [ PPC-06 600 mg BID] [Placebo]

Subject Number	In Full Analysis Set?	In Safety Population?	In PP Population?	Reason for Exclusion from PP Population
XX-XXX	Yes	Yes	Yes	XXX
XX-XXX	Yes	No	No	XXX
XX-XXX	No	No	No	NA

Generated on XX/XX/XX:XXXX by XXXX/ Uses: XXXX

Listing 16.2.4.1: Demographics and Baseline Characteristics  
 All Randomized Subjects  
 [PPC-06 400 mg QD] [ PPC-06 400 mg BID] [ PPC-06 600 mg BID] [Placebo]

Subject Number	Date of Birth	Age (years)	Sex	Race	Ethnicity	Weight (kg)	Height (cm)	BMI (kg/m  ) [1]	Waist Circumference (cm)	PASI	BSA	IGA [2]
XX-XXX	DDMMYYYYY DDMMYYYYY	XX	M	Asian	NH	XXX	XXX	XX.X	XXX	X	XX.X	X
XX-XXX	DDMMYYYYY	XX	F	White	H	XXX	XXX	XX.X	XXX	X	XX.X	X

Note: BMI = Body Mass Index; PASI = Psoriasis Area and Severity Index; BSA = Body Surface Area; IGA = Investigator's Global Assessment

NH=Not Hispanic or Latino; H=Hispanic or Latino

[1] Baseline BMI is calculated as baseline weight / baseline height.

[2] 0 = Clear; 1=Almost clear; 2=Mild; 3=Moderate; 4=Severe

Generated on XX/XX/XX:XXXX by XXXX/ Uses: XXXX

Listing 16.2.4.2: Prior and Concomitant Medication  
All Randomized Subjects  
[PPC-06 400 mg QD] [ PPC-06 400 mg BID] [ PPC-06 600 mg BID] [Placebo]

Subject Number	Category	WHO Preferred Term (Verbatim Term) / ATC Classification	Indication/ Total Daily Dose/ Unit/Frequency/Route	Start Date (Day)-Stop Date (Day)	Rescue Medication?/ Taken to treat an AE? AE #
XX-XXX	Prior	XXXXXX (xxxxx)/ XXXXXX	XXX/ XX/XX/XXX/XXXX	DDMMYYYY (XX) – DDMMYYYY (XX)	Yes/Yes: 2
XX-XXX	Concomitant	XXXXXX (xxxxx)/ XXXXXX	XXX/ XX/XX/XXX/XXXX	DDMMYYYY (XX) – ONGOING	No/Yes: 3

Note: Study day is calculated relative to the date of first study drug administration (Day 1).

Generated on XX/XX/XX:XXXX by XXXX/ Uses: XXXX

<Programming Note: List medication in ascending start date for each subject.>

Listing 16.2.4.3: Psoriasis Treatment History  
All Randomized Subjects  
[PPC-06 400 mg QD] [ PPC-06 400 mg BID] [ PPC-06 600 mg BID] [Placebo]

Subject Number	Medication Name	Start Date (Day) - Stop Date (Day)
XX-XXX	XXXXXXXXXX	DDMMMYYYY (XX) – DDMMMYYYY (XX)
	XXXXXXXXXXXX	DDMMMYYYY (XX) – DDMMMYYYY (XX)
	XXXXXXXXXXXX	DDMMMYYYY (XX) – ONGOING

Note: Study day is calculated relative to the date of first study drug administration (Day 1).

Generated on XX/XX/XX:XXXX by XXXX/ Uses: XXXX

<Programming Note: List medication in ascending start date for each subject.>

Listing 16.2.4.4: Concurrent Procedures  
 All Randomized Subjects  
 [PPC-06 400 mg QD] [ PPC-06 400 mg BID] [ PPC-06 600 mg BID] [Placebo]

Subject Number	Preferred Term/ System Organ Class/ Procedure	Diagnosis	Procedure Start Date (Day) - Stop Date (Day)
XX-XXX	XXXXXXXXXX/ XXXXXX/ XXXXXX	XXXXXXXX	DDMMYYYY (XX) – DDMMYYYY (XX)
XX-XXX	XXXXXXXXXX/ XXXXXX/ XXXXXX	XXXXXXXXXXXX	DDMMYYYY (XX) – ONGOING

Note: Study day is calculated relative to the date of first study drug administration (Day 1).

Generated on XX/XX/XX:XXXX by XXXX/ Uses: XXXX

<Programming Note: List medication in ascending start date for each subject.>

Listing 16.2.4.5: Medical/Surgical History  
All Randomized Subjects  
[PPC-06 400 mg QD] [ PPC-06 400 mg BID] [ PPC-06 600 mg BID] [Placebo]

---

Subject Number	Condition/Surgery/Procedure	System Organ Class/ Preferred Term	Procedure Start Date (Day) - Stop Date (Day)
XX-XXX	XXXX	XXXXXX/ XXXXXXX	DDMMMYYYY (XX) – DDMMMYYYY (XX)
XX-XXX	XXXX	XXXXXX/ XXXXXXX	DDMMMYYYY (XX) – ONGOING

---

Generated on XX/XX/XX:XXXX by XXXXXX / Uses: XXXX

Listing 16.2.4.6: Psoriasis Medical History  
All Randomized Subjects  
[PPC-06 400 mg QD] [ PPC-06 400 mg BID] [ PPC-06 600 mg BID] [Placebo]

---

Subject Number	Date of Initial Diagnosis of Plaque Psoriasis	Other Anatomical Areas Affected by Psoriasis
XX-XXX	YYYY	Scalp
XX-XXX	YYYY	Other: XXXXX

---

Generated on XX/XX/XX:XXXX by XXXXX/ Uses: XXXX

Listing 16.2.5.1: Study Drug Accountability – Blister Packs  
 All Randomized Subjects  
 [PPC-06 400 mg QD] [ PPC-06 400 mg BID] [ PPC-06 600 mg BID] [Placebo]

Subject Number	Kit Number	Blister Number	Date (Day) Returned [1]	Number of Tablets Returned
XX-XXX	XXXXXXXX	Week 1	DDMMYYYYY(XX)	XX
		Week 2	DDMMYYYYY(XX)	XX
		Week 3	DDMMYYYYY(XX)	XX
		Week 4	DDMMYYYYY(XX)	XX
		Week 5	DDMMYYYYY(XX)	XX
XX-XXX	XXXXXXXX	Week 1	DDMMYYYYY(XX)	XX
		Week 2	DDMMYYYYY(XX)	XX
		Week 3	DDMMYYYYY(XX)	XX
		Week 4	DDMMYYYYY(XX)	XX

[1] Study day is calculated relative to the date of first study drug administration (Day 1).

Generated on XX/XX/XX:XXXX by XXXXXX / Uses: XX

Listing 16.2.5.2 Study Drug Accountability – Bottles  
 All Randomized Subjects  
 [PPC-06 400 mg QD] [ PPC-06 400 mg BID] [ PPC-06 600 mg BID] [Placebo]

Subject Number	Kit Number	Bottle Number	Date (Day) Returned [1]	Number of Tablets		
				Dispensed	Returned	Used
XX-XXX	XXXXXXXX	AM1	DDMMMYYYY(XX)	30	XX	XX
		AM2	DDMMMYYYY(XX)	60	XX	XX
		PM1	DDMMMYYYY(XX)	30	--	--
		PM2	DDMMMYYYY(XX)	60	XX	XX
XX-XXX	XXXXXXXX	DDMMMYYYY(XX)	DDMMMYYYY(XX)	XX	XX	XX
		DDMMMYYYY(XX)	DDMMMYYYY(XX)	XX	XX	XX
		DDMMMYYYY(XX)	DDMMMYYYY(XX)	XX	XX	XX
		DDMMMYYYY(XX)	DDMMMYYYY(XX)	XX	XX	XX

[1] Study day is calculated relative to the date of first study drug administration (Day 1).

Generated on XX/XX/XX:XXXX by XXXXXX / Uses: XX

Listing 16.2.5.3: Study Drug Exposure and Compliance  
All Randomized Subjects  
[PPC-06 400 mg QD] [ PPC-06 400 mg BID] [ PPC-06 600 mg BID] [Placebo]

Subject Number	Study Period	Total # of Days Exposed [1]	Total # of Expected Tablets	Total # of Tablets Taken [2]	Average Daily Dose of IP [3]	Compliance	
						%Compliance [4]	Compliant?
XX-XXX	Overall	XX	945	XX	XX	XX.X	Yes
	Titration	-	147	XX	-	XX.X	No
	Treatment	-	798	XX	-	XX.X	Yes
XX-XXX	Overall	XX	945	XX	XX	XX.X	No
	Titration	-	147	XX	-	XX.X	Yes
	Treatment	-	798	XX	-	XX.X	Yes

Note: Titration Period: Week 1 – 5. Treatment Period: Week 6 – 24. Overall: Week 1 – 24.

[1] Defined as date of last dose of study drug during the study minus date of first dose of study drug plus 1.

[2] Defined as the summation of number of tablets taken during the titration, treatment, or overall period.

[3] Calculated as the number of tablets divided by the number of days exposed to study medication for the overall period.

[4] Calculated as the number of tablets taken divided by the expected number of tablets, defined for the titration period, treatment period, and overall.

Generated on XX/XX/XX:XXXX by XXXXX / Uses: XX

Listing 16.2.6.1.1: Psoriasis Area and Severity Index (PASI) Score  
 All Randomized Subjects  
 [PPC-06 400 mg QD] [ PPC-06 400 mg BID] [ PPC-06 600 mg BID] [Placebo]

Subject Number	Analysis Visit	Date (Study Day) [1]	Type	Head and Neck	Upper Limbs	Trunk	Lower Limbs	Scores
XXX-XXX	Baseline	DDMMYYYYY(XX)	Erythema	X	X	X	X	XX
			Induration	X	X	X	X	XX
			Scaling	X	X	X	X	XX
			Sum (E+I+S)	X	X	X	X	XX
			Area Involved	X	X	X	X	
			Sum X Area	XX	XX	XX	XX	XX.X
	Week 4	DDMMYYYYY(XX)	Erythema	X	X	X	X	XX
			Induration	X	X	X	X	XX
			Scaling	X	X	X	X	XX
			Sum (E+I+S)	X	X	X	X	XX
			Area Involved	X	X	X	X	
			Sum X Area	XX	XX	XX	XX	XX.X

< continue for other visits >

[1] Study day is calculated relative to the date of first study drug administration (Day 1).

Listing 16.2.6.1.2: PASI Total Score and Change from Baseline and Responders  
All Randomized Subjects  
[PPC-06 400 mg QD] [ PPC-06 400 mg BID] [ PPC-06 600 mg BID] [Placebo]

Subject Number	Analysis Visit	Date (Study Day) [1]	Type	PASI Total Score			PASI-50? [2]	PASI-75? [2]
				Value	CFBL	%CFBL		
XXX-XXX	Baseline	DDMMYYYY (XX)	Observed	60	-	-	-	-
	Week 4	DDMMYYYY (XX)	Observed	52	-8	13.3	N	N
	Week 8	DDMMYYYY (XX)	Observed	40	-20	33.4	N	N
	Week 12	-	LOCF	40	-20	33.4	N	N
		-	m-NRI	-	-	-	N	N

<continue for other visits>

Note: PASI=Psoriasis Area and Severity Index; LOCF=Last Observation Carried Forward; m-NRI= Modified Non-Responder Imputation. CFBL=Change from baseline calculated as post-baseline minus baseline.

[1] Study day is calculated relative to the date of first study drug administration (Day 1).

[2] PASI-50/PASI-75 responder is defined as achieving a reduction of 50%/75% or greater from baseline.

Generated on XX/XX/XX:XXXX by XXXX / Uses: XX

Listing 16.2.6.2: Investigator's Global Assessment (IGA) of Disease Severity  
 All Randomized Subjects  
 [PPC-06 400 mg QD] [ PPC-06 400 mg BID] [ PPC-06 600 mg BID] [Placebo]

Subject Number	Analysis Visit	Visit Date (Day) [1]	Type	IGA Score	IGA Responder?[2]
XX-XXX	Baseline	DDMMMYYYY(XX)	Observed	3 – Moderate	--
	Week 4	DDMMMYYYY(XX)	Observed	2 – Mild	N
	Week 8	-	LOCF	2 – Mild	N
		-	m-NRI	-	N
	Week 12 Etc.	DDMMMYYYY(XX)	Observed	1 – Almost clear	Y

<continue for other visits>

Note: LOCF=Last observation-carried forward; m-NRI= Modified Non-Responder Imputation.

[1] Study day is calculated relative to the date of first study drug administration (Day 1).

[2] IGA responder is defined as achieving an IGA score of clear or almost clear (IGA score 0 or 1).

Generated on XX/XX/XX:XXXX by XXXXX / Uses: XXXX

Listing 16.2.6.3: Investigator's Assessment of the Body Surface Area (BSA) Involvement of Psoriasis  
 All Randomized Subjects  
 [PPC-06 400 mg QD] [ PPC-06 400 mg BID] [ PPC-06 600 mg BID] [Placebo]

Subject Number	Analysis Visit	Visit Date (Day) [1]	Type	Skin Area Involved (Number of Palms)					
				Head and Neck	Upper Limbs	Trunk	Lower Limbs	Total	
								Value	CFBL
XX-XXX	Baseline	DDMMYYYY(XX)	Observed	0	2	1	1	3	--
	Week 4	DDMMYYYY(XX)	Observed	X	X	X	X	X	X
	Week 8	DDMMYYYY(XX)	Observed	--	--	--	--	--	--
			LOCF	X	X	X	X	X	X

<continue for other visits>

Note: LOCF=Last observation-carried forward. CFBL=Change from baseline: calculated as post-baseline minus baseline.  
 [1] Study day is calculated relative to the date of first study drug administration (Day 1).

Generated on XX/XX/XX:XXXX by XXXXX / Uses: XXXX

Listing 16.2.6.4.1: Nail Psoriasis Severity Index (NAPSI) at Baseline  
 All Randomized Subjects  
 [PPC-06 400 mg QD] [ PPC-06 400 mg BID] [ PPC-06 600 mg BID] [Placebo]

Subject Number	Visit Date	Hand/ Digit	Nail Bed					Nail Matrix					Total					
			1	2	3	4	5	1	2	3	4	5	1	2	3	4	5	
XX-XXX	DDMMYYYY	Left/1	X	X	X	X	X	X	X	X	X	X	X	X	X	X*	X	X
		Right/1	X	X	X	X	X	X	X	X	X	X	X	X	X	X	X	X

Generated on XX/XX/XX:XXXX by XXXXX / Uses: XXXX

[Programming Note: put a star next to the total score of the selected target nail]

Listing 16.2.6.4.2: Target Nail Psoriasis Severity Index (NAPSI)  
 All Randomized Subjects  
 [PPC-06 400 mg QD] [ PPC-06 400 mg BID] [ PPC-06 600 mg BID] [Placebo]

Subject Number	Analysis Visit	Visit Date (Day) [1]	Nail Bed Score	Nail Matrix Score	Total score		CFBL	
					Observed	LOCF	Observed	LOCF
XX-XXX	Baseline	DDMMMYYYY(XX)	X	X	X	-	-	-
	Week 12	DDMMMYYYY(XX)	X	X	X	-	X	-
	Week 16	-	-	-	-	X	-	X
	Week 24	DDMMMYYYY(XX)	X	X	X	-	X	-
	Etc.							

CFBL=Change from baseline calculated as post-baseline minus baseline.

[1] Study day is calculated relative to the date of first study drug administration (Day 1).

Generated on XX/XX/XX:XXXX by XXXXX / Uses: XXXX

Listing 16.2.6.5: Psoriasis Scalp Severity Index (PSSI)  
 All Randomized Subjects  
 [PPC-06 400 mg QD][ PPC-06 400 mg BID][ PPC-06 600 mg BID][ Placebo]

Subject Number	Analysis Visit	Visit Date (Day) [1]	Type	Erythema	Induration	Scaling	Area scoring	Total	
								Value	CFBL
XX-XXX	Baseline	DDMMYYYY(XX)	Observed	0	2	1	1	3	--
	Week 4	DDMMYYYY(XX)	Observed	X	X	X	X	X	X
	Week 8	-	LOCF	X	X	X	X	X	X
	Week 12	DDMMYYYY(XX)	Observed	X	X	X	X	X	X
	Etc.								

Note LOCF=Last observation-carried forward; CFBL=Change from baseline: calculated as post-baseline minus baseline.

[1] Study day is calculated relative to the date of first study drug administration (Day 1).

Generated on XX/XX/XX:XXXX by XXXXX / Uses: XXXX

Listing 16.2.6.6: Palmoplantar Physician's Global Assessment of Disease Severity (PP PGA)  
All Randomized Subjects  
[PPC-06 400 mg QD] [ PPC-06 400 mg BID] [ PPC-06 600 mg BID] [Placebo]

Subject Number	Analysis Visit	Visit Date (Day) [1]	Type	Value	CFBL
XX-XXX	Baseline	DDMMYYYYY(XX)	Observed	3 – Moderate	--
	Week 4	DDMMYYYYY(XX)	Observed	2 – Mild	-1
	Week 8	DDMMYYYYY(XX)	Observed	2 – Mild	-1
	Week 12	DDMMYYYYY(XX)	Observed	1 – Almost clear	-2
	Week 16	DDMMYYYYY(XX)	Observed	1 – Almost clear	-2
XX-XXX	Baseline	DDMMYYYYY(XX)	Observed	3 – Moderate	--
	Week 4	DDMMYYYYY(XX)	Observed	3 – Moderate	X
	Week 8	DDMMYYYYY(XX)	Observed	2 – Mild	-1
	Week 12	--	LOCF	2 – Mild	-1
	Week 16	DDMMYYYYY(XX)	Observed	XXX	X
	Week 20	DDMMYYYYY(XX)	Observed	XXX	X
	Week 24	DDMMYYYYY(XX)	Observed	XXX	X

Note: LOCF=Last observation-carried forward. CFBL=Change from baseline calculated as post-baseline minus baseline.

[1] Study day is calculated relative to the date of first study drug administration (Day 1).

Generated on XX/XX/XX:XXXX by XXXXX / Uses: XXXX

Listing 16.2.6.7: Itch by NRS  
 All Randomized Subjects  
 [PPC-06 400 mg QD] [ PPC-06 400 mg BID] [ PPC-06 600 mg BID] [Placebo]

Subject Number	Analysis Visit	Visit Date (Day) [1]	Type	Value	CFBL
XXX-XXX	Baseline	DDMMYYYY (XX)	Observed	X	-
	Week 4	DDMMYYYY (XX)	Observed	X	X
	Week 8	-	LOCF	X	X
	Week 12	DDMMYYYY (XX)	Observed	X	X
	Week 16	DDMMYYYY (XX)	Observed	X	X
	Week 20	DDMMYYYY (XX)	Observed	X	X
	Week 24	DDMMYYYY (XX)	Observed	X	X
	<Etc.>				

Note: NRS = Numerical Rating Scale. LOCF=Last observation-carried forward. CFBL=Change from baseline calculated as post-baseline minus baseline.

[1] Study day is calculated relative to the date of first study drug administration (Day 1).

Generated on XX/XX/XX:XXXX by XXXX/ Uses: XXXX

Listing 16.2.6.8: Self-Report Quick Inventory of Depressive Symptomatology (QIDS-SR16)  
All Randomized Subjects  
[PPC-06 400 mg QD] [ PPC-06 400 mg BID] [ PPC-06 600 mg BID] [Placebo]

Subject Number	Analysis Visit	Visit Date (Day) [1]	Q1	Q2	Q3	Q4	Q5	Q6	Q7	Q8	Q9	Q10	Q11	Q12	Q13	Q14	Q15	Q16	Total	
																			Value	CFBL
XX-XXX	Baseline	DDMMMYYYY(XX)	0	0	0	2	1	1	1	3	0	1	1	1	1	1	1	1	X	X
	Week 12	DDMMMYYYY(XX)	1	1	1	3	2	1	1	3	1	1	1	1	1	1	1	1	X	X
	Week 16	DDMMMYYYY(XX)	1	0	0	1	0	0	0	1	1	0	0	0	0	0	0	0	X	X
	Week 24	DDMMMYYYY(XX)	1	0	0	1	0	0	0	1	1	0	0	0	0	0	0	0	X	X
	Etc.																			

Note: CFBL=Change from baseline calculated as post-baseline minus baseline.

1. Falling asleep; 2. Sleep during the night, 3. Waking up too early; 4. Sleeping too much 5. Feeling sad, 6. Decreased appetite, 7. Decreased appetite 8. Decreased weight (within the last two weeks), 9. Increased weight (within the Last two weeks), 10. Concentration/decision making, 11. View of myself, 12. Thoughts of death or suicide,13. General interest, 14. Energy level, 15. Feeling slowed down, 16. Feeling restless

[1] Study day is calculated relative to the date of first study drug administration (Day 1).

Generated on XX/XX/XX:XXXX by XXXXXX / Uses: XXXX

Listing 16.2.6.9.1: Dermatology Life Quality Index (DLQI) Individual Questions  
 All Randomized Subjects  
 [PPC-06 400 mg QD] [ PPC-06 400 mg BID] [ PPC-06 600 mg BID] [Placebo]

Subject Number	Analysis Visit	Visit Date (Day) [1]	Q1	Q2	Q3	Q4	Q5	Q6	Q7	Q8	Q9	Q10
XX-XXX	Baseline	DDMMMYYYY(XX)	X	X	X	X	X	X	X	X	X	X
	Week 12	DDMMMYYYY(XX)	X	X	X	X	X	X	X	X	X	X
	Week 16	DDMMMYYYY(XX)	X	X	X	X	X	X	X	X	X	X
	Week 24	DDMMMYYYY(XX)	X	X	X	X	X	X	X	X	X	X
	Etc.											

[1] Study day is calculated relative to the date of first study drug administration (Day 1).

Generated on XX/XX/XX:XXXX by XXXXX / Uses: XXXX

Listing 16.2.6.9.2: Dermatology Life Quality Index (DLQI) Domains and Total Score  
 All Randomized Subjects  
 [PPC-06 400 mg QD] [ PPC-06 400 mg BID] [ PPC-06 600 mg BID] [Placebo]

Subject Number	Analysis Visit	Visit Date (Day) [1]	Symptoms and Feelings		Daily Activities		Leisure		Work and School	Personal Relationships		Treatment	Total	
			Value	CFBL	Value	CFBL	Value	CFBL	Value	Value	CFBL	Value	Value	CFBL
XX-XXX	Baseline	DDMMYYYY(XX)	X	--	X	--	X	--	X	X	--	X	X	--
	Week 12	DDMMYYYY(XX)	X	X	X	X	X	X	X	X	X	X	X	X
	Week 16	DDMMYYYY(XX)	X	X	X	X	X	X	X	X	X	X	X	X
	Week 24	DDMMYYYY(XX)	X	X	X	X	X	X	X	X	X	X	X	X
XX-XXX	Baseline	DDMMYYYY(XX)	X	--	X	--	X	--	X	X	--	X	X	--
	Week 12	DDMMYYYY(XX)	X	X	X	X	X	X	X	X	X	X	X	X
	Week 16	DDMMYYYY(XX)	X	X	X	X	X	X	X	X	X	X	X	X
	Etc													

Note: CFBL=Change from baseline calculated as post-baseline minus baseline.

Symptoms and Feelings includes Q1 and Q2; Daily Activities includes Q3 and Q4; Leisure includes Q5 and Q6; Work and School includes Q7 and Q7a; Personal Relationships includes Q 8 and Q9; Treatment includes Q10

[1] Study day is calculated relative to the date of first study drug administration (Day 1).

Generated on XX/XX/XX:XXXX by XXXXX / Uses: XXXX

Listing 16.2.6.10.1: SF-12 Subdomains  
 All Randomized Subjects  
